9.4 Secondary Analyses

Postoperative STAI-State and postoperative VAS are each analyzed using ANCOVA with the following model:

$$\text{Outcome_T3} = \beta_0 + \beta_1 \times \text{Group} + \beta_2 \times \text{Baseline} + \beta_3 \times \text{Age} + \beta_4 \times \text{Sex} + \epsilon$$

Where Baseline = STAI-State_T1 or VAS_T1, respectively. The homogeneity-of-slopes assumption is evaluated prior to each ANCOVA by testing the Group \times Baseline interaction. If violated for a secondary endpoint, the J–N procedure is applied analogously to the primary analysis. ANCOVA is selected for its robustness to deviations from normality given the sample size ($n > 30$ per group); where Shapiro–Wilk indicates substantial departure from normality, a non-parametric supportive analysis (Mann–Whitney U on change scores or rank-based ANCOVA) is reported.

9.5 Sensitivity Analyses

- Per-Protocol analysis: the primary analysis (Path A or Path B) is repeated in the PP set.
- Unadjusted analysis: independent-samples t-test (or Mann–Whitney U) on T2 lnRMSSD without baseline or covariate adjustment.
- Covariate-minimal model: Path A or Path B fitted without age and sex, to assess covariate contribution.
- Influence diagnostics: standardized residuals from the primary model are inspected; analyses are repeated excluding observations with $|\text{standardized residual}| > 3$.

9.6 Subgroup Analyses (Exploratory)

Exploratory subgroup analyses examine consistency across: sex (male/female), age (< 60 vs. ≥ 60 years), and surgical procedure type. Results are exploratory and are interpreted descriptively without multiplicity adjustment.

10. Handling of Missing Data

Missing data are not anticipated for the primary endpoint, given that intraoperative HRV is recorded continuously throughout the surgical procedure. Should missing or invalid data occur, the following rules apply:

- HRV signal validity: epochs containing artifact are excluded prior to RMSSD computation. Participants must have $\geq 75\%$ valid R-waves throughout the intraoperative recording to be included in the primary analysis. Participants below this threshold are treated as having missing primary outcome data.

- Missing post-test STAI or VAS: participants with missing T3 values for a secondary endpoint are excluded from the analysis of that endpoint only, with missingness reported by group.
- Primary endpoint missingness $\leq 5\%$: complete-case analysis is reported as the primary analysis.
- Primary endpoint missingness $> 5\%$: multiple imputation ($m = 50$) under a missing-at-random (MAR) assumption is used as the primary approach, with complete-case analysis reported as a sensitivity analysis. A tipping-point sensitivity analysis is additionally reported.

11. Handling of Multiplicity

There is a single primary endpoint (intraoperative InRMSSD), tested at $\alpha = 0.05$ (two-sided). No multiplicity adjustment is required for the confirmatory inference.

The two secondary endpoints (postoperative STAI-State and postoperative VAS) are interpreted as supportive, with each tested at the nominal $\alpha = 0.05$ without multiplicity adjustment. Conclusions regarding secondary endpoints are framed accordingly. No formal hierarchical or gatekeeping testing procedure is applied.

12. Interim Analyses and Data Monitoring

No formal interim analyses involving statistical testing of the study hypotheses are planned. No formal stopping rules are prespecified. A Data Monitoring Committee is not established for this low-risk, non-pharmacological behavioral intervention.

13. Safety Considerations

This trial evaluates a low-risk, non-pharmacological intervention. No drug-related safety endpoints are prespecified. Adverse events potentially related to the surgical procedure or the intervention are recorded descriptively in the Safety Set. No inferential testing of safety outcomes is planned.

14. Specification Status of Analytical Elements

In the interest of full transparency, this section identifies the prospective specification status of each analytical element described in this SAP. Elements are categorized into three groups:

Analytical Element	Specification Status
Primary outcome (intraoperative HRV)	Prospectively specified in the ClinicalTrials.gov registration on December 15, 2024, prior to first-participant enrollment.
Secondary outcomes (STAI-State, VAS)	Prospectively specified in the ClinicalTrials.gov registration.
Directional hypothesis (IG > CG on InRMSSD)	Prospectively specified.
Eligibility criteria	Prospectively specified in the IRB-approved protocol and trial registration.
Randomization 1:1 with statistician blinding	Prospectively specified.
Sample size justification ($n = 74$)	Prospectively specified in the IRB-approved protocol.

ANCOVA as base analytic framework	Prospectively specified in the IRB-approved protocol.
Natural log transformation of RMSSD	Standard methodological convention (Laborde et al., 2017); applied prior to outcome modeling.
Inclusion of age and sex as covariates	Methodological refinement during the analysis phase, in line with standard recommendations for HRV research (Quigley et al., 2024). Applied uniformly to primary and secondary analyses prior to outcome modeling.
Johnson–Neyman procedure (Path B)	Methodological response to observed violation of the homogeneity-of-regression-slopes assumption (Hayes, 2022; Ji, 2016). The Johnson–Neyman procedure is the recognized standard analytical follow-up when the moderator is continuous and ANCOVA's homogeneity-of-slopes assumption is violated.
75% R-wave validity threshold	Methodological standard derived from Sheridan et al. (2020); applied uniformly to all participants.
Subgroup and sensitivity analyses	Exploratory; documented in this SAP.
Allocation concealment description	Clarified during manuscript preparation; reflects the actual procedure implemented since trial commencement, with no change in practice.

Critically, the primary outcome, the directional hypothesis, the analytic intent, and the eligibility criteria are unchanged from the prospectively registered ClinicalTrials.gov record (NCT06742814) and the IRB-approved protocol (202408018RIND). The methodological refinements documented above (inclusion of age and sex as covariates; application of the Johnson–Neyman procedure following observed assumption violation) do not constitute changes to the primary outcome or to the directional hypothesis. They represent transparent, methodologically grounded responses applied uniformly to the analysis.

15. Reporting

The trial is reported in accordance with the CONSORT 2025 Statement (Hopewell et al., 2025) and the TIDieR checklist. The primary publication includes: (i) a CONSORT 2025 flow diagram; (ii) a baseline characteristics table by group; (iii) the primary analysis results, with explicit indication of which analysis path (A or B) was followed and the homogeneity-of-slopes test outcome; (iv) secondary endpoint results in the same format; (v) sensitivity and subgroup analyses; and (vi) safety summary. The publication will further document the specification status of each analytical element consistent with Section 14 of this SAP.

16. References

- Hayes, A. F. (2022). Introduction to mediation, moderation, and conditional process analysis: A regression-based approach (3rd ed.). Guilford Press.
- International Council for Harmonisation. (2019). E9(R1) Addendum on Estimands and Sensitivity Analysis in Clinical Trials.
- Ji, X. R. (2016). A primer on the Johnson–Neyman technique: An alternative procedure to ANCOVA. *General Linear Model Journal*, 42(1), 18–25.
- Karatas, T. C., & Gezginci, E. (2023). The effect of using a stress ball during endoscopy on pain, anxiety, and satisfaction: A randomized controlled trial. *Gastroenterology Nursing*, 46(4), 309–317.

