2.3 Hypotheses

Compared with the control group, the intervention group is hypothesized to demonstrate:

- H1 (Primary): Higher intraoperative lnRMSSD, reflecting enhanced parasympathetic modulation.
- H2 (Secondary): Lower postoperative state anxiety scores.
- H3 (Secondary): Lower postoperative pain intensity scores.

3. Study Design

This is a single-center, two-arm, parallel-group, statistician-blinded, randomized controlled trial reported in accordance with the CONSORT 2025 Statement (Hopewell et al., 2025). Participants are randomly allocated 1:1 to the intervention group (IG) or the control group (CG).

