3.3 Intervention

All participants receive standard perioperative nursing care under local anesthesia using a mixture of 5 mL of 2% lidocaine, 5 mL of normal saline, and 0.1 mL of epinephrine (1 mg/mL), yielding an approximate final epinephrine concentration of 1:100,000, without tourniquet.

Following completion of all baseline assessments (T1), participants in the IG receive a commercially available soft foam stress ball (6 cm in diameter, moderate resistance) in their non-operative hand. A trained research assistant delivers standardized verbal instructions, asking participants to squeeze the ball rhythmically at a rate of once every three seconds while focusing attention on the ball, with the opportunity to practice before entering the operating room. The intervention commences at the initiation of surgery and continues until completion. Participants in the CG rest the non-operative hand naturally on the arm board without any object.

4. Sample Size Justification

(Prospectively specified in the IRB-approved protocol.)

Sample size was determined a priori using G*Power v3.1.9 ($\alpha = 0.05$ two-tailed; power = 0.80). Because no prior randomized controlled trial had examined the effect of stress ball use on HRV-based outcomes at the time of trial design, an effect size of Cohen's $d = 0.71$, derived from post-procedure pain scores in a randomized controlled trial of stress ball use during unsedated endoscopy (Karatas & Gezginci, 2023), was used as the reference effect size. This study was selected as the closest available proxy given its use of the same intervention in a comparable invasive procedural context.

The calculation indicated that 64 participants (32 per group) would be required to detect the reference effect. Allowing for an anticipated 10% attrition rate, the target enrollment was set at 74 participants (37 per group). The acknowledged limitation that the reference effect size derives from a subjective pain outcome rather than an HRV-specific endpoint is discussed in the limitations section of the primary publication.

5. Analysis Populations

The following analysis populations are defined for this analysis:

Population	Definition
Full Analysis Set / ITT	All randomized participants, analyzed according to the group to which they were randomized regardless of intervention received. The FAS is the primary analysis population for all efficacy endpoints.

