8.2 Significance Level and Confidence Intervals

All hypothesis tests are two-sided with a nominal significance level of $\alpha = 0.05$. Confidence intervals are reported at the 95% level.

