9.3 Primary Analysis (Conditional on Homogeneity-of-Slopes Test)

The primary analysis examines intraoperative lnRMSSD using a regression model that includes group, baseline lnRMSSD, the Group \times Baseline lnRMSSD interaction term, age, and sex. The homogeneity of regression slopes assumption is evaluated by the significance of the Group \times Baseline lnRMSSD interaction term. The analysis path is conditional on this test:

Path A — Interaction not significant ($p \geq .05$)

If the homogeneity-of-slopes assumption holds, the interaction term is removed and a standard ANCOVA is fitted:

$$\ln\text{RMSSD_T2} = \beta_0 + \beta_1 \times \text{Group} + \beta_2 \times \ln\text{RMSSD_T1} + \beta_3 \times \text{Age} + \beta_4 \times \text{Sex} + \epsilon$$

Results are reported as adjusted means (SE) per group, the adjusted between-group mean difference (IG – CG) with 95% CI, the F-statistic with degrees of freedom, p-value, and partial eta squared (η^2).

Path B — Interaction significant ($p < .05$)

If the homogeneity-of-slopes assumption is violated, the conditional treatment effect across the range of baseline lnRMSSD values is examined using the Johnson–Neyman (J–N) procedure (Hayes, 2022; Ji, 2016) — the standard methodological response to violation of the homogeneity-of-slopes assumption when the moderating variable is continuous. The full moderation model is retained:

$$\text{lnRMSSD_T2} = \beta_0 + \beta_1 \times \text{Group} + \beta_2 \times \text{lnRMSSD_T1} + \beta_3 \times (\text{Group} \times \text{lnRMSSD_T1}) + \beta_4 \times \text{Age} + \beta_5 \times \text{Sex} + \epsilon$$

Results are reported as: (i) the overall model F-statistic and R^2 ; (ii) the Group \times Baseline lnRMSSD interaction F-statistic, p-value, and ΔR^2 ; (iii) the J–N region(s) of significance; and (iv) the proportion of the analyzed sample that falls within each region. Conditional simple effects are plotted across the observed range of baseline lnRMSSD.

The primary analysis is performed in the FAS (ITT).

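### Johnson–Neyman (Path B) was added after unequal slopes were observed, yet Sections 7, 9.3 and 11 let it carry the confirmatory test of H1 and drop the ANCOVA effect when it is triggered

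*Combined protocol and SAP*

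**What the plan says.** **When each element was specified.** The SAP is Version 1.0, dated May 10, 2026; the trial was registered on December 15, 2024. The Section 14 table attributes ANCOVA, as the base framework, to the IRB-approved protocol. It describes Path B as a "Methodological response to observed violation of the homogeneity-of-regression-slopes assumption", and the closing paragraph of that section again places Path B after an observed violation. Age and sex are recorded as added during the analysis phase. For those covariates and for the log transformation, the table says they were applied before outcomes were modelled; it makes no such statement for Path B. Only subgroup and sensitivity analyses are marked exploratory.

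**What role Path B has.** Section 9.3 regresses T2 lnRMSSD on group, baseline lnRMSSD, their product, age and sex. If the product term has p ≥ .05, it is removed and the ANCOVA (Path A) is reported with its adjusted mean difference. If p < .05, "the conditional treatment effect across the range of baseline lnRMSSD values is examined" by Johnson–Neyman. The Path B outputs are overall model fit, the interaction test, the regions of significance and the share of the sample in each region. In that case Section 7 makes the regions the population-level summary of the primary estimand.

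**What is claimed.** Section 8.2: "All hypothesis tests are two-sided with a nominal significance level of" 0.05. Section 11: "No multiplicity adjustment is required for the confirmatory inference". The closing paragraph of Section 14 says that "the primary outcome, the directional hypothesis, the analytic intent, and the eligibility criteria are unchanged" from the registration and the IRB-approved protocol. Section 15 commits the publication to state which path was followed, the result of the slopes test and the specification status of each element.

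**The concern.** An analysis adopted because of a pattern in the outcome data cannot be a confirmatory test in the same data. H1 (Section 2.3) is an overall directional statement: lnRMSSD is higher in the intervention group (IG). Path B replaces it with ranges of baseline lnRMSSD, and no section says which pattern of regions would confirm or refute H1.

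Section 14 reports the violation as already observed, so the rule in Section 9.3 leads to Path B. From then on the plan does not require the adjusted mean difference to be reported. The per-protocol and covariate-minimal analyses in Section 9.5 follow the same path. The only overall comparison left is the unadjusted t-test or Mann–Whitney test. At stake is the trial's headline conclusion.

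**Working it through.** **1. Order of events.** The slopes test in Section 9.3 is the Group × Baseline coefficient in a model whose response is T2 lnRMSSD. A violation can therefore be observed only after the primary outcome has been fitted by group. Section 14 says Path B responded to such an observation, so Path B entered the plan after that fit. Sections 7 and 9.3 present the same branch as a forward rule, and Section 11 calls the inference confirmatory. These statements do not fit together.

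**2. The plan's own figures.**
- Sample size (Section 4: d = 0.71, two-sided 0.05, power 0.80, 1:1): 2 × (1.960 + 0.842)² / 0.71² = 15.70 / 0.5041 = 31.1, so 32 per arm and 64 in total, as stated. With the noncentral t distribution, power is 79.8% at 32 per arm and 81.1% at 33.
- Attrition of 10%: 64 / 0.90 = 71.1, so 72; 66 / 0.90 = 73.3, so 74. The stated 74 is within two participants of the first figure and equals the second.
- This sample size is for an overall mean difference, not an interaction. It is not in dispute here.

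**3. Error rate of the two-path rule.** From the SAP: the Section 9.3 model with age and sex, two-sided 0.05, 1:1 allocation, N = 64 and 74. Assumed, because the SAP gives no values: normal data, baseline–outcome slope (correlation) of 0.3 or 0.6, and Path B counted as positive if any observed baseline value lies in a region of significance. There is no treatment effect at any baseline. Each setting has 20,000 simulated trials.

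| N | Slope | ANCOVA alone | Interaction p < .05 | Two-path rule | Path B part |
|---|---|---|---|---|---|
| 64 | 0.3 | 0.050 | 0.049 | 0.094 | 0.047 |
| 64 | 0.6 | 0.051 | 0.048 | 0.094 | 0.045 |
| 74 | 0.3 | 0.051 | 0.049 | 0.094 | 0.046 |
| 74 | 0.6 | 0.049 | 0.053 | 0.097 | 0.050 |

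The Monte Carlo standard error is √(0.095 × 0.905 / 20,000) ≈ 0.002. As a cross-check, two independent tests at 0.05 give 1 − 0.95² = 0.0975. A further set of runs that added N = 66 put the upper end at 0.099.

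ANCOVA alone reproduces the stated 0.05 (0.049–0.051). False positives favouring IG rise from 0.025–0.026 with ANCOVA alone to 0.054–0.057 with the two-path rule.

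**4. Given a significant interaction under the null.** In the first row, 0.04665 / 0.04945 = 94% of trials show a region in some direction, and 0.02965 / 0.04945 = 60% show one favouring IG. Over the four settings these figures are 94–95% and 60–65%. The further runs gave 92–96% and 62–68%.

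**The case against.** **Disclosure.** Section 14 states openly where Path B came from, and Section 15 commits the publication to repeat it. This deserves credit, and it rules out reading the plan as concealment. It does not make the branch confirmatory while Sections 7, 9.3 and 11 still give it that role.

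**Blinding.** Section 3.2 keeps groups coded A and B until the primary analysis is finalized. Coding may have hidden the direction of effect, so the documents do not show that Path B was chosen because it favoured IG. Coding does not hide whether slopes differ, and no section says that Path B was fixed before unmasking.

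**Unequal slopes invalidate ANCOVA.** Johnson–Neyman is a recognised follow-up, and its use as such is not disputed. But the ANCOVA effect is (ȳ_IG − ȳ_CG) − b(x̄_IG − x̄_CG), with b the pooled slope. Randomization makes the expected baseline difference zero, so this still targets the average difference that H1 concerns when slopes differ.

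**Stronger readings that a reader might infer.**
- That ANCOVA has no confirmatory role at all. Path A is that ANCOVA and is primary when slopes are homogeneous; it loses its role only when Path B is triggered.
- That the claim of unchanged analytic intent is false. The term is undefined and the IRB-approved protocol is not among these documents, so it cannot be shown whether that protocol required a slopes check. The claim is unsupported, not disproved.
- That the figure of about 94% measures the cost of hindsight, or shows that H1 almost always succeeds. The simulation would give the same result had Path B been specified before enrolment, and it counts regions in either direction.

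**Conclusion.** The point stands. By the SAP's own account, a branch added after the slopes had been seen is the primary analysis and primary estimand summary, under a confirmatory label at 0.05. The ANCOVA effect that was specified in advance drops out when that branch is triggered.

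Under no effect, the two-path rule has two-sided type I error of about 0.094–0.099, against about 0.05 for ANCOVA alone. After a significant interaction, a region in some direction appears in about 92–96% of null trials and one favouring IG in about 60–68%. These figures rest on normal data, N of 64–74, an assumed baseline slope of 0.3–0.6 and the any-region success rule, since the SAP defines none. They describe the rule; any further cost of choosing it after seeing the data comes on top and is not estimated.

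**What to change.** - **Sections 7, 9.3 and 11:** make the ANCOVA group effect (adjusted difference, 95% CI, two-sided 0.05) the only confirmatory test of H1, reported whatever the slopes test shows.
- **Covariates:** use those the IRB-approved protocol names. If it does not name age and sex, use group plus baseline lnRMSSD, and report the age- and sex-adjusted model as a sensitivity analysis. Otherwise a covariate set added during the analysis phase would keep the confirmatory label.
- **Sections 7, 9.3, 14 and 15:** label Path B and its regions post hoc and exploratory.
- **Section 14, closing paragraph:** replace the unchanged-intent wording with a statement that the primary-endpoint analysis was extended after the slope violation was observed. Give the dates of data lock, first slopes test and unmasking relative to SAP Version 1.0.

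The cost is SAP and manuscript wording plus a reanalysis of data in hand. The downside is real: if the ANCOVA is null, the headline is null and Johnson–Neyman is hypothesis-generating only.
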